7.5.2.3 Respiratory event and other time-to-event endpoints

A 'time to respiratory event' composite endpoint consists of the following events:

- A decrease of one or more points from baseline in any of the ALSFRS-R respiratory function subdomain scores (items 10–12).
- Starting non-invasive mask ventilation (NIV).
- Meeting 'protocolised' criteria for NIV: SVC (supine) $\leq 50\%$ predicted.
- Invasive mechanical ventilation by intubation.
- Invasive mechanical ventilation by tracheostomy.
- Death.

Time to respiratory event is reached whenever any of the criteria has first been met.

The following time-to-event secondary efficacy variables will be evaluated using Cox's proportional hazards regression:

1. Time to tracheostomy, continuous ventilator dependence, or death (TRCVDDTH)
2. Time to NIV or death (NIVDEATH)
3. Time to respiratory event (RESPEVNT)

Individual components of all the composite endpoints will be analysed in the same fashion:

1. Time to continuous ventilator dependence (ALSFRS-R item 12 ≤ 1 ; CVD)
2. Time to decline from baseline in any ALSFRS-R respiratory domain score (FRSBR1D)
3. Time to SVC (supine) $\leq 50\%$ of predicted (SVC50PP)
4. Time to non-invasive mask ventilation (NIV)
5. Time to intubation (INTUB)
6. Time to tracheostomy (TRACH)
7. Time to death (DEATH)

As will these additional endpoints derived from the SVC and ALSFRS-R values:

1. Time to decline from baseline SVC (supine) by $\geq 20\%$ (SVC20PD)
2. Time to decline from baseline ALSFRS-R total score by $\geq 20\%$ (FRS20PD)
3. Time to continuous use of NIV during the night (ALSFRS-R item 12 ≤ 2)

The data for the time-to-event variables will be stored in the ADTTE dataset with parameter names corresponding to those in parentheses above.

The analysis model will include an effect for treatment, and will be adjusted for randomization strata. Premature discontinuations will be treated as right-censored in the analyses. Censoring rules for different scenarios are described in **Error! Reference source not found..** For the purpose of determining the end date, survival and ventilation status are considered to be assessed daily; ALSFRS-R and SVC measurements are assessed only on study visits. For composite

endpoints, the date of last assessment is defined to be the latest date at which the endpoint can be fully assessed: that is, the earliest date in the set of latest assessments of each of its component endpoints.

Table 2. Censoring rules for time-to-event analyses.

Scenario	Censored	End date
Event criteria fulfilled	No	Date of endpoint assessment
Event criteria fulfilled at baseline	Yes	Date of randomization
Event criteria never assessed	Yes	Date of randomization
Completed Week 48 without event	Yes	Date of last endpoint assessment
Discontinued study	Yes	Date of last endpoint assessment
Discontinued study treatment (1 day after*)	Yes	Date of last endpoint assessment
Died, when death not part of event criteria	Yes	Date of last endpoint assessment
Died, when death is part of event criteria	No	Date of death

*) to account for potential events following immediately after the study treatment discontinuation.

SAS code in the following fashion will be used to fit the statistical models:

```
proc phreg data = ADTTE;
  where ITTFL = "Y" and PARAMCD = "RESPEVNT";
  class TRTP(ref = "PLACEBO") STRATAR;
  model AVAL * CNSR(1) = TRTP STRATAR / ties = efron rl;
run;
```

For descriptive purposes, Kaplan-Meier survival curves will be plotted in addition to the statistical analysis results from the Cox models. Also, restricted mean survival time (RMST) will be described graphically at 14-day intervals from start of follow-up up to 48 weeks. These analyses are used to visually inspect the plausibility of the proportional hazards assumption.

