6.1.3 Telephone contacts

The study centre personnel will phone the subjects during weeks 18, 30 and 42. During the phone call ALSFRS-R will be assessed and AEs inquired.

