Tipping point analyses will be considered for further evaluating sensitivity of the results with respect to missing data. In such an analysis, the distribution of missing data in the active treatment group would be shifted by varying amounts, until a point is found where the results of the analysis cross the threshold of statistical significance specified in section 6.2.2. The plausibility of a shift of the found size is then used to assess the robustness of results to unobserved differences due to missing data.

Subjects who discontinue study treatment but remain in the study can continue to contribute ALSFRS-R data, which will be included in the analyses where applicable. However, in time-to-

event analyses subjects will be censored from follow-up one day after study treatment discontinuation.

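### The respiratory-event composite counts late events but censors event-free subjects at the last full assessment, so censoring depends on the outcome; the effect is small and one derivation rule removes it

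*SAP*

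**What the plan says.** SAP 7.5.2.3 defines the event by its first component: "Time to respiratory event is reached whenever any of the criteria has first been met". In Table 2, a subject who meets the criteria is uncensored at "Date of endpoint assessment". A subject who completes Week 48 event-free, leaves the study or stops treatment is censored at "Date of last endpoint assessment". For composites, that date is "the earliest date in the set of latest assessments of each of its component endpoints".

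The components are not observed equally often: "survival and ventilation status are considered to be assessed daily; ALSFRS-R and SVC measurements are assessed only on study visits". Under Table 1 of the protocol, SVC is taken at Weeks 2, 4, 8, 12, 24, 36 and 48, and ALSFRS-R at Weeks 4, 8, 12, 24, 36 and 48. Protocol 6.1.3 adds telephone contacts in Weeks 18, 30 and 42: "During the phone call ALSFRS-R will be assessed and AEs inquired". Under Protocol 6.6, remote visits at Weeks 36 and 48 drop SVC but keep ALSFRS-R and ventilation and survival status. SAP 7.10.3 expects missing SVC, mainly at Week 48.

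Two other rules bear on this. SAP 6.2.5 says that in time-to-event analyses "subjects will be censored from follow-up one day after study treatment discontinuation". The same section lists time to respiratory event among the endpoints analysed with multiple imputation.

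**The concern.** An event is dated by one component, but remaining event-free is credited only up to the date when all components were last known. No rule limits events to that date. Time between the last full assessment and the end of follow-up is thus counted for subjects who then have an event and removed for those who do not. A Cox model and a Kaplan-Meier estimate both assume that, within strata, the censoring time carries no information about the event. Here it does.

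The endpoint is second in the secondary hierarchy (SAP 6.2.3) and is one of two used for futility (SAP 6.2.13). The Kaplan-Meier and restricted-mean displays, which SAP 7.5.2.3 uses to check proportional hazards, inherit the distortion. The composite of tracheostomy, continuous ventilator dependence or death has a visit-based component too and follows the same rule.

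**Working it through.** **The plan's own figure.** The only design figure for this endpoint is power of about 70% (SAP 5: 450 subjects, levosimendan event rate 73%, hazard ratio 0.70, log-rank). The placebo rate is 1 − 0.27^(1/0.70) = 84.6%. Expected events are 450 × (2/3 × 0.73 + 1/3 × 0.846) = 346. Schoenfeld power is Φ(√(346 × 2/9) × |ln 0.70| − 1.96) = 87.8%. With 360 subjects it is 79.9%. A comparison of Week 48 proportions in 360 subjects gives 70.5%, which may be where the figure comes from. This is a separate matter, and nothing below rests on it.

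**One subject, two outcomes.** A subject stops drug at Week 32. The last SVC was at Week 24 and the last ALSFRS-R was by telephone at Week 30.
- Event-free: censored at Week 24.
- Respiratory item drop at Week 30: event at Week 30.
- NIV started at Week 31: event at Week 31.

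Weeks 24 to 32 are at risk only if the subject fails. If telephone contacts are not study visits under SAP 7.5.2.3, the second case falls away but the third remains.

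**Simulation inputs.** From the documents: visit schedule, 2:1 allocation, 73% event rate, hazard ratio 0.70. Assumed: component shares ALSFRS-R/SVC/ventilation or death of 50/25/25 (also 70/15/15 and 34/33/33), the stopping rates, and the missing-SVC rate. Imputation was not simulated. The comparator ends follow-up at drug stop or Week 48 whatever the event status.

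| Stopping, levosimendan vs placebo | HR, SAP rule | HR, common end date |
|---|---|---|
| 20% vs 20% | 0.703 | 0.703 |
| 30% vs 15% | 0.710 | 0.704 |
| 40% vs 20% | 0.709 | 0.700 |
| 10% vs 30% | 0.694 | 0.702 |

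Rows come from separate large runs, so compare across a row, not down a column. The other component shares give similar shifts.

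With 20% stopping in each arm:
- Week 48 event rate, SAP rule vs common date: levosimendan 73.5% vs 73.1%, placebo 84.8% vs 84.5%.
- Event-free discontinuers lose about 4 weeks of follow-up on average.
- Events after the last full assessment are about 1% of all events.
- Power is 85.8% under both rules.

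Under the null (3,000 trials of 450 per scenario, equal and unequal stopping), type I error was 4.2 to 5.5% with the SAP rule and 4.2 to 5.4% with the common date, a difference within simulation error.

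**Missing Week 48 SVC, by hand.** Take the levosimendan arm with a constant hazard, no stopping, and a fraction m = 0.30 (assumed) lacking an unimputed Week 48 SVC.
- Event-free at Week 36: 0.27^0.75 = 0.375.
- Event-free from Week 36 to 48: c = 0.27^0.25 = 0.721.
- Probability of a non-SVC event in that interval: q = 1 − 0.721^0.75 = 0.218.
- SAP rule: subjects lacking the SVC stay at risk after Week 36 only if they fail, so the estimate is 0.375 × (0.70 × 0.721)/(0.70 + 0.30 × 0.218) = 24.7%, against 27.0%.
- Common end date: 0.375 × (0.70 × 0.721 + 0.30 × 0.782) = 27.7%.

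At m = 0.20 and 0.40 the SAP rule gives 25.6% and 23.6%. The simulation at 30% missing, which also includes stopping, puts the levosimendan event rate 2.5 to 3.2 points too high and the placebo rate 1.9 to 2.1 points too high, measured against cutting both events and censoring at the last full assessment.

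**The case against.** The strongest reply is that the asymmetry does not reach the inference. With equal stopping, the hazard ratio and power do not move. The Kaplan-Meier curves are descriptive, and the test is from the Cox model. This stands.

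The hazard-ratio shift also needs unequal stopping between SVC visits. The protocol's heart-rate stopping criterion (4.5, 5.3.2) is judged mainly on pre-dose ECGs at clinic visits, where supine SVC is also taken pre-dose; a stop there leaves little or no SVC gap. Placing the excess levosimendan stops at scheduled visits cuts the shift from 0.009 to about 0.003 (40% vs 20%) and to about 0.002 (30% vs 15%). This stands too. If levosimendan has more stops, the rule is conservative for superiority.

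Imputation may close the gap for a planned SVC that was missed, such as a remote Week 48 visit. It cannot do so at Weeks 18, 30 and 42, where no SVC is planned. For subjects who stop drug, SAP 6.2.5 ends follow-up anyway. The analysis without imputation (SAP 7.5.4.4) remains exposed.

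A reader might infer a real loss of power. Runs of 600 simulated trials gave 78% vs 81% at 40% vs 20% stopping, and 85% vs 87% at 30% vs 15%. Each figure has a standard error of 1.4 to 1.7 points, and no paired error is available. The size is arithmetically possible: with 315 events, Schoenfeld power is 84.7% at a hazard ratio of 0.700 and 82.1% at 0.709. The inputs lack support, however. These splits mean overall stopping of (2 × 40 + 20)/3 = 33% and (2 × 30 + 15)/3 = 25%, against the plan's dropout allowance of about 20%, and no document gives a split by arm.

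**Conclusion.** The flaw is in the text: for this composite, censoring depends on the outcome. Its effect is small.
- **Equal stopping:** hazard ratio, power and type I error essentially unchanged; event-free probability about 0.3 to 0.4 points too low.
- **Unequal stopping (assumed 30% vs 15% to 40% vs 20%):** hazard ratio shifts about 0.006 to 0.009 against the arm with more stops, and less if the extra stops occur at clinic visits.
- **Week 48 SVC missing in an assumed 20 to 40%:** a larger Kaplan-Meier shift, about 2.5 to 3 points at 30%, mainly where nothing is imputed.

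These sizes rest on assumed component shares, stopping rates and missing-SVC rates. The documents do not support reading this as material bias in the treatment effect or as type I error inflation. It is still worth correcting, because the rule is wrong in principle and easy to change before unblinding.

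**What to change.** In SAP 7.5.2.3 and Table 2, define one end-of-follow-up date for each subject that does not depend on event status: the earliest of one day after treatment discontinuation, study discontinuation, and Week 48, as far as ventilation and survival status are known. Count events up to that date and censor event-free subjects on it. Apply it to the death row as well, which now carries no such limit although SAP 6.2.5 ends follow-up one day after drug stop. State how imputed SVC values enter the Table 2 dates, and whether telephone contacts count as study visits. Use the same rule for the other composites with visit-based components.

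The cost is one derivation rule and a few sentences. The downside is small: SVC events in the last interval between visits, or at a missed and unimputed Week 48 SVC, may go unseen. With 30% missing, that makes event-free probability too high by about 0.5 to 0.7 points (0.4 to 1.0 across the component shares tried), less than the present error and in the opposite direction.

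Cutting events as well as censoring at the last full assessment would also restore symmetry, but it should not be the main analysis. It would discard observed deaths and NIV starts, against the endpoint definition in Protocol 6.2.3.

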4.5 Removal of subjects from treatment or assessment

Study subjects are free to discontinue the study at any time without providing a reason. However, the investigator should try to identify the reason and document it in the CRF.

A subject must discontinue the study treatment for the following reasons:

- HR increase of > 30 bpm from baseline (visit 1) at the dose level of 1 mg once daily in 3 separate ECG recordings, taken within 5-10 minutes from each other before the morning dose of the study drug (see also section 6.5.4).
- Life-threatening supraventricular or ventricular arrhythmia.
- The investigator judges that it is in the best interest of the subject to stop the study treatment due to any other abnormality compromising patient safety. However, the investigator should consult the medical monitor whenever possible in these instances.
- Pregnancy.
- Invasive mechanical ventilation by intubation or tracheostomy.

The subjects who have discontinued the study medication, but continue in the study, are encouraged to follow the study visit and phone call schedule according to the study protocol for recording ALSFRS-R, ventilatory support and survival status. End-of-study visit assessments for these subjects will be performed 14-25 d after the last study treatment administration.

A subject must discontinue the study if the investigator or the sponsor considers the discontinuation to be medically necessary or in the best interest of the subject.

Irrespective of the reason for discontinuation, the subject should be invited to end-of-study assessments as soon as possible. As long as the subject consents, all relevant assessments, at least those of safety, should be performed, preferably according to the schedule for the end-of-study assessments.

The study monitor should be notified about premature discontinuations by email/phone/fax within 24 hours in the event of discontinuation due to an SAE (see section 6.5.1.3) or within 7 days in the event of discontinuation due to another reason.

DNO 090017ff823c9bac / 1.0 Approved 22 / 58

Subjects who prematurely discontinue will not be replaced. Discontinued subjects are not allowed to re-enter the study.

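### For the supportive endpoint of continuous ventilator dependence (and, for intubation alone, its composite), starting invasive ventilation usually censors the subject as event-free

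*SAP*

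**What the plan says.** Four rules act together.

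- **Treatment stop.** Protocol 4.5 lists "Invasive mechanical ventilation by intubation or tracheostomy" among the reasons for which a subject must discontinue study treatment.
- **End of follow-up.** SAP 6.2.5 states that in time-to-"event analyses subjects will be censored from follow-up one day after study treatment discontinuation". Table 2 in SAP 7.5.2.3 repeats this in the row beginning "Discontinued study treatment (1 day after": the subject is censored, and the end date is the last endpoint assessment. The table's footnote explains the extra day as an allowance for events that come straight after the drug is stopped.
- **Definition of CVD.** SAP 7.5.2.3 lists the component beginning "Time to continuous ventilator dependence (ALSFRS-R item 12", with threshold ≤ 1. No ventilation record enters the definition. For end dates, "survival and ventilation status are considered to be assessed daily", whereas "ALSFRS-R and SVC measurements are assessed only on study visits".
- **Composite.** SAP 7.5.2.3 lists "Time to tracheostomy, continuous ventilator dependence, or death (TRCVDDTH"). Intubation is not a component. A composite's last assessment is "the earliest date in the set of latest assessments of each of its component endpoints".

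SAP 7.5.2 places neither CVD nor TRCVDDTH in the testing hierarchy and treats everything outside the hierarchy as supportive.

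**The concern.** The event that can make a subject ventilator dependent also stops the drug, and stopping the drug closes the observation window before the next ALSFRS-R can record the dependence. The one-day allowance suits outcomes dated to the day, such as death or the start of ventilation. It does not suit a scale scored every four to six weeks.

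Censoring is then informative: subjects leave the CVD risk set because their respiratory function failed, and they leave as event-free. A Cox model assumes that censored subjects have the same later hazard as comparable subjects still followed, and here they do not. If the groups differed in invasive ventilation, the CVD hazard ratio would miss most of that difference among subjects without an earlier item 12 ≤ 1. A reader would also expect an endpoint with this name to include subjects on invasive ventilation.

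**Working it through.** The plan states no figure for this endpoint, so there is nothing to reproduce. The check applies the rules to two hypothetical records and then counts days in the schedule.

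**Inputs.** Protocol Table 1 and section 6.1.3 give nine post-baseline ALSFRS-R assessments: centre visits at Weeks 4, 8, 12, 24, 36 and 48, and telephone contacts at Weeks 18, 30 and 42. Planned sample size is 450 (Protocol 4.1).

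**Record A: tracheostomy on Day 200, no earlier item 12 ≤ 1.** The drug stops on Day 200 and follow-up ends on Day 201. The last ALSFRS-R was at Week 24 (Day 169); the next is at Week 30 (about 30 × 7 + 1 = Day 211).
- CVD: censored at Day 169.
- TRCVDDTH: event on Day 200, through tracheostomy.
- RESPEVNT (time to respiratory event): event by Day 200 at the latest.

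**Record B: intubation without tracheostomy on Day 100, no earlier item 12 ≤ 1.** Follow-up ends on Day 101. The last ALSFRS-R was at Week 12 (Day 85); the next is at Week 18 (about 18 × 7 + 1 = Day 127).
- CVD: censored at Day 85.
- TRCVDDTH: survival and tracheostomy status are known to Day 101 and CVD to Day 85. The earliest of these is Day 85, so the subject is censored there, subject to the point about later death under the objection.
- RESPEVNT: event by Day 100 at the latest.

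**Chance that an ALSFRS-R catches the event.** Assume ventilation starts on a day spread evenly over 48 × 7 = 336 days, the drug stops the same day, and an assessment counts only on that day or the next. Each assessment then covers 2 days.
- All nine assessments: 9 × 2 / 336 = 18/336 = 5.4% captured, 94.6% missed.
- Six centre visits only, if telephone contacts are not study visits: 6 × 2 / 336 = 12/336 = 3.6% captured, 96.4% missed.

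**How far back the censoring date moves.** For a gap of g days between assessments, the days since the last assessment sum to (g − 2)(g − 1)/2, counting captured days as zero.
- Nine assessments (three gaps of 28 days, six of 42): (3 × 351 + 6 × 820)/336 = 5973/336 = 17.8 days on average, maximum 40.
- Centre visits only (three gaps of 28, three of 84): (3 × 351 + 3 × 3403)/336 = 11262/336 = 33.5 days on average, maximum 82.

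**Number of subjects.** The documents give no rate of intubation or tracheostomy. At an assumed 1–3% over 48 weeks, 450 × 0.01 = 4.5 and 450 × 0.03 = 13.5 subjects start invasive ventilation. Multiplying by 0.946 gives 4.3 to 12.8, or about 4–13 lost from CVD. This is a ceiling, because anyone with an earlier item 12 ≤ 1 is already an event. For TRCVDDTH only intubations without tracheostomy are at issue, so the number is smaller.

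**Does anything else recover the event?** The multiple-imputation list in SAP 6.2.5 includes time to respiratory event but neither CVD nor TRCVDDTH. The end-of-study visit has no ALSFRS-R (Protocol Table 1 and 6.1.5). ALSFRS-R collected after drug stop is kept for other analyses by SAP 6.2.5, but time-to-event follow-up has already ended.

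**The case against.** A reader might infer that invasively ventilated subjects drop out of the trial's respiratory results, or that a confirmatory comparison is biased. The documents support neither. Intubation and tracheostomy are both components of RESPEVNT, the only time-to-event endpoint in the hierarchy. Each also has its own analysis (INTUB and TRACH) on status treated as known daily. Tracheostomy counts directly in TRCVDDTH. That TRCVDDTH comes first in the SAP's list of time-to-event variables gives it no testing priority.

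Three further objections have weight.

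- **Size.** Subjects who pass through continuous non-invasive ventilation may already have scored item 12 ≤ 1. Their share is unknown, so the count is only an upper bound.
- **Later death.** Death is a component of TRCVDDTH, and Table 2 has a row that counts it as an event. The table does not say which row prevails when drug stop comes first. An intubated subject who later dies may or may not count, so Record B's TRCVDDTH result is not certain in that case.
- **Construct.** SAP 7.5.2.1 derives CVD from the ALSFRS-R, and leaving intubation out of TRCVDDTH may be deliberate. Counting every intubation would widen both endpoints and admit short, reversible episodes.

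These narrow the point and bear on the choice of remedy. They do not answer it for CVD: even if the item 12 definition is intended, the cut-off prevents item 12 from being read after ventilation starts.

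**Conclusion.** The point holds for CVD, and for TRCVDDTH only in subjects intubated without tracheostomy. In subjects with no earlier item 12 ≤ 1, about 95% of such first events are missed (96% if telephone assessments do not count), and the subject is censored event-free at the previous ALSFRS-R. The percentage rests on evenly spread onset and a same-day drug stop. The ceiling of about 4–13 of 450 subjects rests on an assumed 1–3% rate.

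The effect on the hazard ratio, including its direction, cannot be computed from the documents. The primary endpoint and all hierarchical secondaries are untouched by this route. This is a low-priority but real derivation fault in supportive endpoints.

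**What to change.** Amend SAP 7.5.2.3 for CVD and TRCVDDTH in one of two ways.

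1. Count the recorded start date of intubation or tracheostomy as meeting CVD when it precedes item 12 ≤ 1, and carry this into TRCVDDTH. Add a sensitivity analysis that does not count short, reversible intubations, with the criterion for these set before unblinding.
2. Keep the item 12 definition, but do not end follow-up at study drug stop for these two endpoints. Protocol 6.1.6 and SAP 6.2.5 show that ALSFRS-R continues to be collected.

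The first option costs one sentence and one line in the ADTTE derivation and uses dates already collected. Its drawback is that some reversible intubations count in the main analysis. The second preserves the construct but depends on ALSFRS-R being obtained after discontinuation, which the protocol only encourages. With either option, Table 2 should state which row prevails when drug stop is followed by death. Neither option changes the treatment-stopping rule.

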8.4.3 Analysis of efficacy

The primary efficacy variable SVC (supine) will be compared between the treatment arms using the MMRM with between subject effects for treatment, centre and randomisation strata, time as within subject effect, and baseline value (visit 1) as a covariate. Primary efficacy will be evaluated at 12 weeks using contrasts to obtain estimates from the primary model including all SVC measurements prior to 12 weeks. Any missing data will be imputed using multiple imputation method. Effect of missing data imputation will be evaluated analysing observed data only and estimating the slope of decline using the random slope model. Several sensitivity subgroup analyses will be performed and defined in the SAP. Additional evaluations will be performed including all data through 48 weeks, using the MMRM.

DNO 090017ff823c9bac / 1.0 Approved 46 / 58

SD = standard deviation

Secondary efficacy endpoints will be tested in following hierarchy to preserve the overall alpha level:

- 1. Combined assessment of ALSFRS-R function and survival through 48 weeks
- 2. Time to respiratory event through 48 weeks
- 3. CGI through 48 weeks
- 4. Supine Borg CR 10 scale at 12 weeks
- 5. Slope of decline in respiratory function of ALSFRS-R through 48 weeks

The efficacy variables time to respiratory event, time to NIV or death, time to SVC (supine) decline of 20%, time to SVC (supine) \leq 50% of predicted, time to ALSFRS-R total score decline of 20% and time to decline in ALSFRS-R respiratory domain will be evaluated using the Cox's proportional regression model. The model will include effect for treatment and will be adjusted for randomisation strata. Premature discontinuations will be censored from the analyses. Censoring rules will be defined in the SAP.

The efficacy variables ALSFRS-R total score and its subdomain scores will be performed through 48 weeks. Primary analysis will combine change from baseline to 48 weeks and survival through 48 weeks in joint rank analysis (Berry JD et al., 2013) using Wilcoxon-Mann-Whitney test. Slope of decline will be estimated using the random slope model. Additional analyses will be conducted using the MMRM and estimates for individual time points will be done using contrasts. Imputation of missing data using the multiple imputation method will be considered.

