6.2 Statistical issues

6.2.1 Randomization

Randomization will be conducted centrally using Medidata Rave RTSM. The subjects will be allocated to 2 parallel groups receiving either levosimendan 1-2 mg daily or placebo in 2:1 ratio.

The estimated number of sites is approximately 100 and randomization will not be stratified by centre. Randomization will be stratified by the following factors:

1. Bulbar onset
2. Edaravone use
3. North American region

The stratification variable used to adjust the statistical models will combine all three randomization factors into a single factor with $2^3 = 8$ distinct levels.

Due to data entry errors at randomization, levels of the stratification factors used for randomization may differ from final CRF data. Primary analyses will be conducted with the levels of stratification factors used for randomization (STRATAR in ADSL), while final CRF data will be used in a sensitivity analysis (STRATAV in ADSL; see 7.5.4).

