6.2.9 Multiple timepoints

The primary efficacy model will include all planned post-baseline visits up to the Week 12 visit. Additional analyses of primary efficacy will include all planned study visits. Included timepoints for other endpoints will be described separately. Baseline measurements of outcome variables will be included as covariates in the models. The MMRM will be used to estimate the covariance between measurements for a given subject, without assuming any specific structure a priori. Planned visit will be included as a factor in the model. For slope analyses, the actual study day of the visit will be used. All time-to-event analyses will be performed up to the first event only.

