7.5.2 Secondary efficacy variables

The following secondary efficacy endpoints will be tested in the hierarchy below in order to preserve the overall alpha level:

1. Combined assessment of function and survival (CAFS) through 48 weeks
2. Time to respiratory event
3. Clinical Global Impression (CGI) through 48 weeks
4. Supine Borg CR 10 scale at 12 weeks
5. Slope of change in the ALSFRS-R respiratory domain through 48 weeks

The endpoints and their methods of analysis are described in the following sections. Endpoints and analyses that are not listed in the testing hierarchy are included for supportive purposes only.

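### The Cox model for time to respiratory event leaves out baseline supine SVC, a cheap and probably useful covariate; the planned test is valid, and the power at stake depends on an assumed prognostic strength

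*SAP*

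**What the plan says.** SAP 7.5.2.3 describes the model in words, "The analysis model will include an effect for treatment, and will be adjusted for randomization strata", and codes it as "model AVAL * CNSR(1) = TRTP STRATAR / ties = efron rl". Protocol 8.4.3 has the same two terms: "The model will include effect for treatment and will be adjusted for randomisation strata". SAP 6.2.1 defines the stratum: "The stratification variable used to adjust the statistical models will combine all three randomization factors into a single factor". The three factors are bulbar onset, edaravone use and North American region, giving eight levels. None is a respiratory measure.

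The composite in SAP 7.5.2.3 mixes two kinds of criterion:

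- One is an absolute threshold, "Meeting 'protocolised' criteria for NIV: SVC (supine"), set at or below 50% of predicted.
- Another is relative to the subject's own start: "A decrease of one or more points from baseline in any of the ALSFRS-R respiratory function subdomain scores (items 10–12").
- The rest are starting NIV, intubation, tracheostomy and death.

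Table 2 of the SAP censors at randomisation anyone who already meets the criteria at baseline.

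SAP 7.5.2 introduces the ordered list of secondary endpoints: "The following secondary efficacy endpoints will be tested in the hierarchy below in order to preserve the overall alpha level". Time to respiratory event is second of five, after CAFS. The primary SVC model in SAP 7.5.1.1 adjusts for baseline supine SVC. For the respiratory event, baseline supine SVC appears only as a median-split subgroup (SAP 6.2.14), where the stratum term is removed. No sensitivity analysis in SAP 7.5.4 adds it to this Cox model.

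**The concern.** Visit 1 supine SVC fixes the distance to the 50% threshold. Entry is restricted on sitting SVC only (60–90%, Protocol 4.2), so the supine value has no entry limit of its own. Protocol 1.2.1 also describes supine vital capacity as a better predictor of survival than upright, and death is another component. The variable is therefore likely to be prognostic for this event, and it is already collected.

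Leaving a prognostic covariate out of a Cox model pulls the estimated treatment hazard ratio towards 1 and lowers power. The endpoint's place in the hierarchy adds weight: if it misses, CGI, supine Borg CR10 and the slope of the ALSFRS-R respiratory domain cannot be claimed. The plan itself puts power here at only about 70%.

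**Working it through.** **1. The plan's own figure.** Inputs (SAP 5, Protocol 8.2): 450 subjects at 2:1 (300/150), 48-week levosimendan event rate 73%, hazard ratio 0.70, two-sided 5%, log-rank test, stated power about 70%.

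- Placebo rate under proportional hazards: 1 − 0.27^(1/0.70) = 84.6%.
- Events: 300 × 0.73 + 150 × 0.846 = 346.
- Schoenfeld: Φ(|ln 0.70| × √(346 × 2/3 × 1/3) − 1.96) = Φ(0.357 × 8.77 − 1.96) = Φ(1.17) = 87.8%.
- With 20% loss (240/120): 277 events, 79.9%.

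The stated 70% is not reproduced. It corresponds to about 219 events, which equals 300 × 0.73, the levosimendan events alone. This is a separate matter, but it means the effect of adjustment should be shown at both event counts.

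**2. Simulated Cox models.** Two-sided 5% Wald test, 300/150, 48 weeks, conditional treatment hazard ratio 0.70, 1,500 trials per row. Baseline SVC is a standard normal covariate. The hazard ratio per SD is an assumption, because the documents give none. The adjusted fit also carried a second, non-prognostic covariate, and strata were left out of both fits.

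| Assumed HR per SD of SVC | About 345 events: unadjusted → adjusted | About 215 events: unadjusted → adjusted |
|---|---|---|
| 1.00 | 89% → 89% | 72% → 71% |
| 1.25 | 87% → 88% | 71% → 72% |
| 1.5 | 84% → 89% | 68% → 72% |
| 2.0 | 74% → 89% | 61% → 71% |

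From the unrounded results the gains are 1.3, 5.7 and 15.2 points in the first column and 0.9, 3.8 and 9.9 in the second. In the prognostic rows the unadjusted hazard ratio runs from 0.70 to 0.74. The Monte Carlo standard error of one power figure near 75% is √(0.75 × 0.25/1500) = 1.1 points, so the gain at 1.25 is barely distinguishable from none.

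**3. Event built from its parts.** Here the prognostic strength comes out of the simulation instead of being chosen. The document input is a placebo fall of 8.5 points in 12 weeks (BENEFIT-ALS row, SAP Table 1). The following are assumed:

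- baseline supine SVC with mean 70 or 75 and SD 12;
- between-subject slope SD 0.4 points per week and measurement SD 5;
- a treatment effect on slope of 0.1 or 0.2 points per week;
- other events unrelated to baseline SVC, at 0.01 to 0.03 per week on placebo and 0.7 times that on levosimendan.

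Subjects at or below 50% at baseline (2% to 5%) are removed, which mirrors the censoring rule. With 800 trials per scenario, SVC alone raises power by 3 to 9 points (smallest gain 92.1% → 95.5%, largest 50.5% → 59.6%). The implied hazard ratio is 1.63 to 2.13 per SD lower SVC.

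A second version used mean 70, SD 10 or 14, and a treatment ratio of 0.7 on slope and on other events, with 300 trials each. Near the plan's event rates it gave 91% → 93% (SD 10) and 87% → 94% (SD 14). With more non-SVC events the gains were 3 and 7 points.

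**4. Sensitivity to calibration.** If the marginal rates are held at 73% and 84.6%, so that the conditional hazard ratio strengthens with the covariate (0.68, 0.66 and 0.62 at 1.35, 1.65 and 2.0 per SD), unadjusted power stays at 90–91% and adjusted power is 91%, 96% and 99%. Adjustment gains under either calibration. Unadjusted power falls as SVC becomes more prognostic only when the 0.70 is read as conditional.

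**The case against.** The strongest reply is that nothing here is wrong. The SAP text, the SAP code and the protocol agree on the model, it is prespecified, and its type I error is sound. All of that stands.

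A reader might see a breach of SAP 6.2.9, which says "Baseline measurements of outcome variables will be included as covariates in the models". The documents do not support that reading well. The sentence sits directly before the description of the MMRM covariance, a composite event time has no baseline value of its own, and the section mentions time-to-event analyses only to say that they stop at the first event. The rule lends support by analogy; it does not create a contradiction.

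A reader might also infer that the baseline ALSFRS-R respiratory score sets the distance to the event. It does not: a subject starting at 12 and one starting at 9 both need a one-point drop on an item. The score may be prognostic, but the documents do not show it.

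Two further points hold. The share of first events that come from the 50% threshold, as opposed to an ALSFRS-R drop, is not given, so the value of SVC as a predictor is uncertain. And censoring at randomisation removes the lowest supine values and narrows the covariate's spread; the simulations in step 3 allow for this, those in step 2 do not. The prespecified subgroup by baseline supine SVC shows that the sponsor recognises the variable, but it does not change the hierarchical test.

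**Conclusion.** The omission is real and worth repairing, as a cheap improvement and not as the correction of an error. Baseline supine SVC bears directly on one component of the event, and no respiratory baseline enters the model. The expected gain in power is nil if SVC is not prognostic, about 1 point at a hazard ratio of 1.25 per SD, 4 to 6 points at 1.5 and 10 to 15 at 2.0. The simulations closest to the endpoint's definition give about 2 to 9 points. All of these rest on assumed baseline spread, slopes and prognostic strength; the direction is secure, the size is not.

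It would go too far to say that a known amount of power is being thrown away, that the planned analysis is biased in a way that invalidates it, or that every respiratory time-to-event endpoint needs the same change. The documents support none of these.

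**What to change.** Before unblinding, add Visit 1 supine SVC (% predicted, continuous) to the PHREG model for RESPEVNT beside STRATAR. List the change in SAP 7.11, since the protocol names only treatment and strata. Keep the planned model as a sensitivity analysis, with the Kaplan-Meier and RMST displays as the unadjusted view.

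The baseline ALSFRS-R respiratory score may be added as a plausible prognostic covariate, but this is optional. Do not carry the change over automatically to components such as intubation or tracheostomy, where events may be few against an eight-level stratum factor.

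The cost is one parameter against roughly 220 to 350 events, a SAP edit and an entry in the list of changes. Missing values should be a small problem: SAP 6.2.7 substitutes the screening value, and the imputation model in SAP 6.2.5 includes the baseline visit. The real downsides are that the reported hazard ratio becomes conditional on baseline SVC and that the model departs from the protocol's wording.
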